9.3.2 Outcome Assessment

Baseline

- Demographics (sex, age at cinacalcet initiation)
- Medical history (underlying renal disease and presence of comorbidities, HNF1 β mutation, history of parathyroidectomy, history of kidney transplant,; and history of hypocalcaemia)

Observation period (spans from baseline to end of study follow-up)

- Dialysis treatment (switch dialysis modality and dialysis discontinuation)
- Cinacalcet use (prevalent or incident user, cinacalcet type (Mimpara or generic), length of cinacalcet use (*prevalent user only*), date of prescription, prescribed dose, dosage forms (tablets or capsules), frequency, length of prescription, date of prescription change, type of prescription change (dose change, drug withheld, drug discontinuation), reason for prescription change (dose titration, non-compliance, adverse event, nausea, vomiting, PTH-low, PTH-high, PTH within target, hypocalcaemia, hypercalcemia, haemodialysis discontinued, parathyroidectomy, kidney transplant, patient refusal, safety finding, product complaint, other)
- Concomitant medication use (phosphate binders (eg, Calcium carbonate/Calcium acetate, Sevelamer, Lanthanum carbonate, sucroferric oxyhydroxide), oral calcium supplementation, vitamin D (eg, Vitamin D3, active vitamin D analogue), dietary calcium intake, rHGH in terms of dose, frequency, route of administration, date first taken, and date last taken)
- Laboratory parameters (PTH, total Ca, ionized Ca, serum phosphorus, albumin, alkaline phosphatase, bicarbonate (HCO₃), 25OH-Vitamin D3 and HNF1 β mutation); and local PTH clinical target and assay range and cCa level definition of hypocalcaemia)
 - Incidence of hypocalcaemia will be identified in two ways: occurrence of laboratory value reporting cCa < 2.1 mmol/L; or reported adverse event due to hypocalcaemia (ie, blood cCa decreased or symptomatic hypocalcaemia)
 - Medical events of parathyroidectomy and kidney transplant(if kidney transplant, additional laboratory parameters, calcinuria, urine calcium/creatinine ratio, and renal ultrasounds will be collected)
 - Physical measurements (height, weight before and after dialysis, vital signs (systolic and diastolic blood pressure before dialysis), Tanner stage)
 - Dialysis treatment (dialysis vintage at time of cinacalcet initiation, dialysis modality, date, dialysis frequency, dialysis dose, duration, dialysate calcium, ionized calcium before dialysis, switched dialysis modality reason, dialysis discontinuation reason; if dialysis modality is peritoneal dialysis, additional parameters (fill volume, number of cycles, duration of cycle, automated or manual)

For physical measurements (except for Tanner stage) and dialysis treatment variables, data will only be collected every 90 days (+ 30 days) following index date. For all other variables, all data available will be collected if available in the observation period.

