8.1 Primary

In a European cohort of paediatric patients with sHPT on maintenance dialysis and using cinacalcet:

1. To describe patient characteristics
2. To describe how cinacalcet is used
3. To describe laboratory values (PTH, cCa, phosphate and albumin) over time
4. To describe the incidence of hypocalcaemia
5. To describe risk factors associated with time to hypocalcaemia event
6. To describe management of hypocalcaemia

9. Research Methods

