9.9 Limitations of the Research Methods

9.9.1 Internal Validity of Study Design

9.9.1.1 Measurement Error(s)/Misclassification(s)

Persistence of medications is quantified by the number of days the medication is available to the patient. This represents a simplified measure, since the definition does not access if the patient takes the medication (ie, compliance/adherence). Nonetheless, in the absence of a valid measure and to maintain consistency and comparability between studies of persistence, the number of days the medication was prescribed to the patient during his/her observation period in this study will be used as a proxy to define persistence.

Hypocalcaemia event is defined by cCa laboratory value and reporting of adverse event due to hypocalcaemia (ie, blood cCa decreased or symptomatic hypocalcaemia). It is possible that hypocalcaemia may be under-reported if a patient did not have both albumin and total serum Ca measured on the same day to calculate cCa. However, we may assume that for those circumstances, hypocalcaemia events (if any occurred) are likely to be asymptomatic. For symptomatic hypocalcaemia events, which result in hospitalisation or medical interventions, these events will be captured as an adverse event.

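### Describing how hypocalcaemia is managed is a primary objective, but dialysate calcium is recorded only on a 90-day grid from index and the only calcium supplement listed is oral

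*Protocol*

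**What the plan says.** Section 8.1 of the protocol makes "To describe management of hypocalcaemia" one of six primary objectives.

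Section 9.3.2 fixes what is collected, and the Abstract repeats it. Three groups of variables could show a response to an event.

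- **Cinacalcet.** Each prescription change carries a date, a type (dose change, withheld, discontinued) and a reason, and hypocalcaemia is one of the reasons.
- **Concomitant medication.** The list covers "phosphate binders (eg, Calcium carbonate/Calcium acetate, Sevelamer, Lanthanum carbonate, sucroferric oxyhydroxide") and then "oral calcium supplementation, vitamin D (eg, Vitamin D3, active vitamin D analogue), dietary calcium intake, rHGH in terms of dose", followed by frequency, route and first and last dates.
- **Dialysis.** The list includes "dialysis dose, duration, dialysate calcium, ionized calcium before dialysis".

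The timing rule separates them. Dialysis variables fall under the rule that "data will only be collected every 90 days (+ 30 days) following index date". For the rest, "For all other variables, all data available will be collected if available in the observation period".

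Section 9.9.1.1 adds: "For symptomatic hypocalcaemia events, which result in hospitalisation or medical interventions, these events will be captured as an adverse event".

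**The concern.** The responses to an event are recorded unevenly. A cinacalcet change or a course of oral calcium can be dated to the day. A temporary change in dialysate calcium is seen only if a scheduled snapshot happens to fall inside it. The snapshot clock starts at index, and nothing in the protocol triggers an extra record when an event occurs. Calcium given by a non-oral route does not appear among the listed variables at all.

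The loss runs in one direction. Non-oral and dialysate responses are under-counted, so cinacalcet and oral responses make up too large a share of what is described. Data that were never abstracted cannot be recovered by an analysis plan, so the point belongs in the protocol.

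**Working it through.** **1. The plan's own figure.** Section 9.5 gives a half-width of 10.1% for N = 70 and an incidence of 25%. The normal approximation gives 1.96 × √(0.25 × 0.75 / 70) = 10.14%, so the figure reproduces and is not in dispute. It is used here only for the number of patients with an event.

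**2. Patients with an event.** 0.25 × 70 = 17.5. Over the range quoted in section 9.5, 0.227 × 70 = 15.9 and 0.28 × 70 = 19.6.

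**3. Chance that a snapshot catches a temporary change.** If a change lasts d days and snapshots are G days apart, with timing unrelated to the event, the chance is min(1, d/G). G is 90 days on schedule and 120 days if every interval stretches by the full 30. If the 30 days are only a window around points fixed from index, average spacing stays at 90 and the right-hand column applies. The durations are **assumptions**; the documents give none.

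| Assumed duration d | G = 120 | G = 90 |
|---|---|---|
| 3 days | 2.5% | 3.3% |
| 7 days | 5.8% | 7.8% |
| 14 days | 11.7% | 15.6% |
| 30 days | 25.0% | 33.3% |
| 60 days | 50.0% | 66.7% |
| 90 days | 75.0% | 100% |

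**4. Scenario.** Suppose each of 17.5 patients has exactly one 14-day change. Then 17.5 × 0.117 = 2.0 to 17.5 × 0.156 = 2.7 are recorded, and about 15 are not. With 30-day changes, 17.5 × 0.25 = 4.4 to 17.5 × 0.333 = 5.8 are recorded. One change per event patient is also an assumption.

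**5. Non-oral calcium.** No arithmetic applies. Route is recorded, but only for the listed classes, and the listed class is already restricted to oral. The calcium-containing binders do not supply a non-oral item.

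**6. Other channels in the protocol.**

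- The adverse event route identifies the event. The sample contingency form in Appendix C has a field marking a medication as event treatment and a narrative, but it is for use when electronic capture is unavailable and is not part of the section 9.3.2 list.
- Events before enrolment go on the medical history eCRF, are reported in aggregate and need no individual safety report (section 11.2). Retrospective-only countries and deceased patients sit wholly in that stream (sections 9.1 and 11).
- A laboratory value below 2.1 mmol/L counts as an event in section 9.3.2 without needing an adverse event report.

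**7. How many patients the fix might involve.** Section 7.2 quotes 64.5 per 100 subject-years in the paediatric trials. At a constant hazard, one on-treatment year gives 1 − exp(−0.645) = 47.5%, and 0.475 × 70 = 33 patients. The figure of 17 may therefore be low.

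**The case against.** The best defence is one of scope. The Abstract's data analysis paragraph says that cinacalcet and other sHPT medications will be summarised after a hypocalcaemia event, and those are the data collected without a grid. On that reading, dialysate and non-oral calcium lie outside the planned summary, and the gap is a limitation to declare. This is fair as a description of the planned table. It does not settle the point, because Objective 6 is worded without that restriction and a reader will take the result as the management of hypocalcaemia.

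Several stronger readings are tempting and are not supported.

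- *All short-lived responses go unseen.* They do not. Short cinacalcet, oral calcium and vitamin D changes are dated, and vitamin D carries its route. Among short-lived responses from listed variables, only dialysate changes suffer from the grid, and lasting ones will show.
- *Non-oral calcium is never captured anywhere.* This holds only for the section 9.3.2 list. Adverse event reports may mention it for some prospective events, and section 11.2 lets the sponsor ask for discharge summaries or chart extracts. The working eCRF is not shown, so it cannot be said that no other form has a treatment field.
- *Nothing but the safety outcome is recorded before enrolment.* Medication and cinacalcet data are abstracted for that period too.
- *Two or three of 17 is the expected yield.* It is a scenario built on assumed durations and one change per event patient.
- *Section 7.2 makes acute treatment the registry's purpose.* It speaks of informing how the risk is minimised, which is not the same as treating an event.

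**Conclusion.** The point holds in a narrow form. Following the protocol as written, most temporary dialysate calcium changes after an event will leave no record, and non-oral calcium has no listed variable, while the other main responses are collected with dates. The direction of the resulting lean, towards oral and cinacalcet management, follows from the text, provided such responses occur. Its size does not: the 12-16% (14 days) and 25-33% (30 days) catch rates rest on assumed durations, and the documents give neither durations nor frequencies. Adverse event reports may fill part of the gap for prospectively reported events, but the protocol does not require treatment as a registry variable there, and laboratory-only and pre-enrolment events are not reliably covered. The sample size and the incidence estimate are unaffected. This is a cheap improvement, not a flaw that stops the registry from meeting its other objectives.

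One neighbouring passage qualifies the statement that drug changes are fully dated. Section 9.3.1 says treatment data end at the first cinacalcet discontinuation, yet also wants later re-initiation captured. Those statements need to be reconciled.

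**What to change.** Change what is recorded, not how patients are treated.

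1. In section 9.3.2 and the Abstract, replace the oral calcium item with calcium supplementation by any route. The existing dose, route and date fields then apply to it.
2. For each hypocalcaemia event, abstract from the routine chart the last dialysate calcium before the event and any change in the following 30 days. Keep the 90-day grid for everything else in the dialysis group.

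The cost is a modest amount of extra chart entry: about 17 patients at 25% of 70, possibly 33 or more at the protocol's own trial rate, plus any recurrent events. No extra tests or visits are needed and the sample size does not change. If the sponsor prefers not to collect these items, the fallback is to state in section 9.9 that Objective 6 covers cinacalcet and the listed medications only.

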9.3.3 Covariate Assessment

Baseline covariates (demographics, medical history, concomitant medication use, and laboratory parameters as defined in [section 9.3.2](#)) will be described.

9.3.4 Validity and Reliability

Study variables stated in this protocol are objective and relevant to the question under study. Variables are parameters which are routinely measured as part of clinical management of paediatric CKD HD patients.

9.4 Data Sources

Study variables stated in this protocol are objective and relevant to the question under study. Variables are parameters which are routinely measured as part of clinical management of paediatric CKD HD patients.

9.5 Study Size

Based on the enrolment experience of the IPDN cohort of children and adolescents on maintenance dialysis over the last 10 years, off-label use of cinacalcet was observed among 5 to 10% of the population, or approximately 50 to 100 paediatric patients (IPDN, unpublished). Following EMA approval, use of cinacalcet is expected to double. According to the paediatric cinacalcet clinical trials ([Schaefer et al. 2017](#); [Sohn et al. 2019](#); [Warady et al. 2019](#)), the incidence of hypocalcaemia ranged from 22.7 to 28.0%. Assuming an incidence of 25%, a target sample size of 70 paediatric patients will provide an estimate of hypocalcaemia incidence with a two-sided confidence interval half-width of 10.1% (ie, two-sided 95% CI: 14.9%, 35.1%) (see [Table 1](#)).

Table 1. Two-sided Confidence Interval Half-widths for Hypothetical Hypocalcaemia Incidence 20%, 25% and 30%, and With Confidence Level at 95%

Confidence Interval Half-width	Hypothetical Hypocalcaemia Incidence		
	20.0%	25.0%	30.0%
Sample size			
50	11.1%	12.0%	12.7%
60	10.1%	11.0%	11.6%
70	9.4%	10.1%	10.7%
80	8.8%	9.5%	10.0%
90	8.3%	8.9%	9.5%
100	7.8%	8.5%	9.0%

9.6 Data Management

Data are abstracted by site staff from patient's medical records into an electronic database provided by the sponsor. The sponsor provides protocol-specific training to all staff delegated to abstract patient data. An eCRF Completion Guideline is provided.

The Amgen representative(s) and regulatory authority inspectors are responsible for contacting and visiting the investigator for inspecting the facilities and, upon request, inspecting the various records of the clinical study (eg, case report forms [CRFs] and other pertinent data) provided that patient confidentiality is respected.

The clinical monitor or designee is responsible for verifying the CRFs at regular intervals throughout the study to verify adherence to the protocol completeness, accuracy, and consistency of the data and adherence to local regulations on the conduct of research. The Clinical Monitor or designee is to have access to patient medical records and other study-related records needed to verify the entries on the CRFs in accordance with the local laws and regulations.

Data capture for this study is planned to be electronic:

- All source documentation supporting entries into the eCRFs must be maintained and available upon request.
- Updates to eCRFs will be automatically documented through the software's "audit trail."
- To ensure the quality of clinical data across all patients and sites, a clinical data management review is performed on patient data received at Amgen. During this review, patient data is checked for consistency, omissions, and any apparent discrepancies. To resolve any questions arising from the clinical data management review process, data queries and/or site notifications are created in the electronic data capture (EDC) system database for site resolution and closed by Amgen reviewer.

The investigator signs only the Investigator Verification Form for this EDC study. This signature indicates that the investigator inspected or reviewed the data on the eCRF, the data queries, and site notifications, and agrees with the content.

9.6.1 Review and Verification of Data Quality

Automatic edit checks within the database and further manual review by the sponsor will help to ensure quality and completeness of the data. Data queries will be sent to sites for clarification and resolution of discrepancies.

9.7 Data Analysis

A Statistical Analysis Plan (SAP) will be developed and will describe all planned analysis in detail. In addition, specifications of tables, figures and listings (TFLs) will be specified.

9.7.1 Planned Analyses

9.7.1.1 Interim Analyses/Analyses

Analyses will be conducted to provide data annually to the EMA **as requested**.

9.7.1.2 Primary Analysis

The primary analysis will be performed at a single time point at the end of the study period (ie, end of data collection 31 December 2023) (see timeline in [section 6](#)).

9.7.2 Planned Method of Analysis

9.7.2.1 General Considerations

There are no formal hypotheses for the study. Descriptive data analyses will be performed. Continuous data will be described using mean, standard deviation (SD), median, interquartile range (IQR) and minimum and maximum values; and categorical variables will be described using counts and frequencies.

Analyses will be performed overall and for two cohorts, incident and prevalent cinacalcet users.

9.7.2.2 Missing or Incomplete Data and Lost to Follow-up

Missing or incomplete data will be reviewed. No imputation of missing data will be performed. When applicable, for continuous variables, the number of nonmissing observations will be presented; and for categorical variables, missing responses will be presented as a separate category.

Patients lost to follow-up will be summarised and censored from analyses, where appropriate.

9.7.2.3 Descriptive Analysis

9.7.2.3.1 Description of Study Enrollment

The number of enrolled patients will be summarised overall and by country.

9.7.2.3.2 Description of Patient Characteristics

Demographics and baseline characteristics (specified in [Section 9.3.2](#)) of patients who initiate cinacalcet and patients who develop and do not develop hypocalcaemia will be summarised.

Treatment characteristics (sHPT medications) at time of first cinacalcet use (*'incident cohort'*) or on 28 August 2017 (*'prevalent cohort'*) will be summarised.

PTH, Ca, P and other relevant laboratory parameters will be described by plotting the median and IQR values every month (30 days) or three months (90 days) following index date and following hypocalcaemia event. Data will be presented overall and stratified by levels of control (eg, low, medium or high of Ca values or mild, moderate or severe PTH levels) at baseline or following hypocalcaemia event (mild, moderate and severe hypocalcaemia) to show the longitudinal trajectory of laboratory values.

To describe time-to-event of first hypocalcaemia event (*incident cinacalcet cohort only*), cinacalcet discontinuation (*incident cinacalcet cohort only*) and cinacalcet re-initiation, KM curves will be plotted, and KM estimates will be calculated. Patients will be censored if they had a kidney transplant, parathyroidectomy or experienced one of the follow-up events ([section 9.2.5](#)), whichever comes first. In the time to hypocalcaemia event analysis, patients will also be censored if they discontinued cinacalcet.

To describe risk factors associated with time to first hypocalcaemia event (*incident cinacalcet cohort only*) after cinacalcet initiation, a multivariate Cox model will be used.

9.7.2.4 Analysis of the Primary Endpoint(s)

Demographics and baseline characteristics (specified in [Section 9.3.2](#)) of patients who initiate cinacalcet and patients who develop and do not develop hypocalcaemia will be summarised.

Treatment characteristics (sHPT medications) at time of first cinacalcet use (*'incident cohort'*) or on 28 August 2017 (*'prevalent cohort'*) will be summarised.

PTH, Ca, P and other relevant laboratory parameters will be described by plotting the median and IQR values every month (30 days) or three months (90 days) following index date and following hypocalcaemia event. Data will be presented overall and stratified by levels of control (eg, low, medium or high of Ca values or mild, moderate or severe PTH levels) at baseline or following hypocalcaemia event (mild, moderate and severe hypocalcaemia) to show the longitudinal trajectory of laboratory values.

To describe time-to-event of first hypocalcaemia event (*incident cinacalcet cohort only*), cinacalcet discontinuation (*incident cinacalcet cohort only*) and cinacalcet re-initiation, KM curves will be plotted, and KM estimates will be calculated. Patients will be censored if they had a kidney transplant, parathyroidectomy or experienced one of the follow-up

events ([section 9.2.5](#)), whichever comes first. In the time to hypocalcaemia event analysis, patients will also be censored if they discontinued cinacalcet.

To describe risk factors associated with time to first hypocalcaemia event (*incident cinacalcet cohort only*) after cinacalcet initiation, a multivariate Cox model will be used.

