9.2.5 Study Follow-up

The registry will record data abstracted from medical charts. Data will be abstracted from the date the patient had a cinacalcet prescription recorded within the study observation period and will continue until death, lost-to-follow-up, transfer to another centre that is not a participating in this registry, turns age 18-years, withdrawal of consent, or end of the study period (ie, 31 December 2023), whichever comes first. Regardless of whether the patient discontinued cinacalcet, follow-up will continue until one of the events described above occurs.

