9.3 Variables

9.3.1 Exposure Assessment

All patients enrolled in the study will have had exposure to cinacalcet. A patient's exposure status will be assessed from the medication history recorded in the patient's medical records (and may be identified by the ATC code for cinacalcet: H05BX01). During the observation period, if a patient discontinues cinacalcet treatment during the study period, the availability of treatment data will end on the date in which cinacalcet was first discontinued. However, data abstraction will continue for other parameters (eg, laboratory parameters, PTH, Ca and P) and will be no different from data collection of patients who are using cinacalcet continuously till the end of the study period or till the occurrence of any event that is described in [section 9.2.5](#). Continuous collection will allow capturing data for patients who may have stopped treatment but re-initiated treatment at a later timepoint. For example, patients who discontinued cinacalcet

because of hypocalcaemia and re-start treatment once Ca levels have returned to normal levels.

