If No, provide stop date: mm ____/dd ____/yyyy ____

Infant date of birth: mm ____/dd ____/yyyy ____

Infant gender: Female Male

Is the infant healthy? Yes No Unknown N/A

If any Adverse Event was experienced by the mother or the infant, provide brief details: _____

Form Completed by:

Print Name: _____

Title: _____

Signature: _____

Date: _____

Protocol Amendment 3

Protocol Title: An Observational Registry Study to Evaluate the use and Safety of Cinacalcet Among Paediatric Patients With Secondary Hyperparathyroidism

Amgen Protocol Number Mimpara® (cinacalcet) 20180204
EU Post Authorisation Study (PAS) Register No. EUPAS24954

Amendment 3 Date: 10 February 2020

Rationale:

- This protocol is being amended to correct a typographical error in [Section 9.2.5](#), where the event of having a parathyroidectomy was mistakenly added as a reason to discontinue follow-up.
- [Section 9.1](#). Study Design updated to ensure that sites know not to enrol a subject until all signatures (as opposed to just the subject's) have been collected on the informed consent form.
- [Section 9.2.1](#). Study Design, Data Collection updated to specify that subjects without a history of prior cinacalcet use should have received at least one dose administration at the time of enrolment.
- [Section 9.2.3.1](#). Inclusion Criteria 101 updated to clarify that age is not at enrolment but at initiation of Cinacalcet.
- [Section 9.2.3.1](#). Inclusion Criteria 102 updated to clarify inclusion criteria wherein patients who have provided written informed consent or notified of participation **(alive or deceased), where required for access to medical charts**, according to local **laws and regulation** requirements.
- [Section 9.7.1.1](#). Interim Analyses/Analyses updated to clarify that analyses will be conducted to provide data annually to the EMA **if requested**, since the European Medicines Agency (EMA) has agreed to have less frequent reports.
- [Section 10.1](#). Informed Consent, Paragraph 1 updated to specify that patient data can be collected retrospectively although the patient is deceased given consent from appropriate parties where required by local regulations.
- [Section 10.1](#). Informed Consent, Paragraph 3 updated to reflect that a parent's signature may be provided given that this is a paediatric study.

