- Hypocalcemia definition: hypocalcemia will be defined according to corrected calcium (cCa) levels as well as by frequency of reported **adverse event (ie, blood decreased Ca or symptomatic hypocalcemia)**. The initial protocol was limited to hospitalization events of hypocalcaemia. This revised definition will increase the sensitivity of detecting hypocalcaemia if hypocalcaemia occurs and the patient is not hospitalised.
- Section 7.2 Rationale: As per EMA feedback, the rationale has been updated to state the following “As part of an agreement with the EMA following marketing authorization , an observational registry will be conducted to describe real-world utilization of cinacalcet and the incidence and risk factors of hypocalcaemia in a cohort of paediatric patients receiving maintenance dialysis with sHPT **in order to inform the management of minimizing this hypocalcaemia risk in clinical practice**”
- Study period includes eligible patients who have initiated or have a record of cinacalcet between 28 August 2017 and 30 June 2023. The observation period ends on 31 December 2023. Patients will have at least 6 months of observation data. For patient eligibility, patient inclusion criteria has been worded more explicitly that we want to include “patients who are aged ≥ 3 - < 18 years on maintenance dialysis **who are diagnosed with sHPT and** have a record of cinacalcet use as per EU marketing authorisation from 28 Aug 2017 to 30 Jun 2023.” This was a suggestion from the EMA feedback. For the exclusion criteria, we have added the following exclusion criteria that states “**Patients who have participated in cinacalcet or etelcalcetide clinical trials**” will be excluded as these patients would not reflect patients who are being treated in routine clinical practice

- For the follow-up and observation period, patients will continue to be followed-up regardless of whether they had a parathyroidectomy event as they may have recurrent disease because of residual parathyroid tissue that was not completely removed and may have recurrent sHPT disease, start on maintenance dialysis and may re-start treatment with cinacalcet.
- Based on UK country-specific feedback, only a retrospective design may be feasible. We have included the following language throughout the protocol, where applicable. "For countries where combination of retrospective and prospective data collection methods is not possible, all data will be collected retrospectively from 31 December 2023."

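### The re-initiation Kaplan-Meier curve is censored at parathyroidectomy and transplant, so it can never count a restart after parathyroidectomy, although follow-up is continued partly because such restarts may occur

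*Protocol*

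**What the plan says.** Section 9.7.2.4, with the same text in 9.7.2.3.2, plans Kaplan-Meier curves for first hypocalcaemia, cinacalcet discontinuation and cinacalcet re-initiation. One rule follows for all three, and the text runs straight from the third curve into it: "cinacalcet re-initiation, KM curves will be plotted, and KM estimates will be calculated. Patients will be censored if they had a kidney transplant, parathyroidectomy" or an end-of-follow-up event of section 9.2.5, whichever comes first. The paragraph does distinguish between curves elsewhere. It limits two of them to incident users, and it adds a rule for one: "In the time to hypocalcaemia event analysis, patients will also be censored if they discontinued cinacalcet". It makes no exception for re-initiation.

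Section 9.2.5 ends follow-up at death, loss to follow-up, transfer to a non-participating centre, age 18, withdrawal of consent or 31 December 2023. Neither procedure is on that list, and the section adds: "Regardless of whether the patient discontinued cinacalcet, follow-up will continue until one of the events described above occurs". Amendment 3 explains that section 9.2.5 was corrected "where the event of having a parathyroidectomy was mistakenly added as a reason to discontinue follow-up".

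Section 9.3.1 gives a purpose for collecting data after a stop: "Continuous collection will allow capturing data for patients who may have stopped treatment but re-initiated treatment at a later timepoint". The Amendment 2 summary of changes says that "patients will continue to be followed-up regardless of whether they had a parathyroidectomy event as they may have recurrent disease", and that they "may have recurrent sHPT disease, start on maintenance dialysis and may re-start treatment with cinacalcet".

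**The concern.** Re-initiation differs from the other two outcomes because it may occur after the censoring event. A child can have a parathyroidectomy, develop recurrent disease and return to cinacalcet. The registry keeps such a child under observation, but the analysis rule takes the child off the curve at the procedure.

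Both procedures are also listed in section 9.3.2 as reasons for a prescription change, and discontinuation is one type of change. Some children will therefore stop at about the time of the procedure that censors them.

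The output at stake belongs to objective 2, how cinacalcet is used. Readers will take the curve as the proportion of children who stop and later restart. Under the stated rule it is something narrower, and the protocol does not say so.

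**Working it through.** **The plan's own figure.** The protocol gives no figure for re-initiation. Its only precision figure is for hypocalcaemia: 1.96 × √(0.25 × 0.75 / 70) = 10.14%, which agrees with the stated 10.1%. The point below does not depend on it.

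**What the rule does, from the text.**

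1. A child is censored at the first of transplant, parathyroidectomy or a 9.2.5 event. A restart dated after either procedure therefore falls after censoring and cannot be an event.
2. The time origin of the re-initiation curve is not stated. If it is the discontinuation date, a procedure on or before that date censors the child at time 0, with no person-time. A child who stops for another reason and has a procedure later contributes time up to the procedure.
3. Kaplan-Meier treats a censored child as having the same later restart rate as children still at risk. Nothing in the protocol supports that for children who have had a transplant.

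**Illustration.** All inputs here are assumed, because the documents give none. Let s be the share of stops due to either procedure (10% to 50%), r the 12-month restart proportion after such stops (0% to 20%) and q the 12-month restart proportion after other stops (30% or 50%). Take the procedure as falling on or before the stop date, with no other censoring.

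- Planned curve at 12 months: q, whatever s and r are.
- Proportion of all stoppers who restart: (1 − s)q + sr.
- Difference: q − [(1 − s)q + sr] = s(q − r).
- Share of actual restarts not on the curve: sr / [(1 − s)q + sr].

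| q | s | r | Planned curve | All stoppers | Restarts not counted |
|---|---|---|---|---|---|
| 30% | 10% | 20% | 30% | 29% | 6.9% |
| 30% | 50% | 20% | 30% | 25% | 40% |
| 30% | 50% | 0% | 30% | 15% | 0% |
| 50% | 10% | 20% | 50% | 47% | 4.3% |
| 50% | 50% | 0% | 50% | 25% | 0% |

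The smallest difference is 0.10 × (0.30 − 0.20) = 1 point and the largest is 0.50 × (0.50 − 0) = 25 points. The share of restarts not counted runs from 0% to 0.10 / 0.25 = 40%. The two maxima come from different rows: the largest difference arises when no one restarts after a procedure, so no restarts are missed there. The sign depends on r against q. The difference is zero when r = q and reverses when r exceeds q.

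**The case against.** **Transplant.** Censoring at transplant can be defended. Criterion 103 requires maintenance dialysis, and restart while still on dialysis and before either procedure is a coherent quantity for a study with no hypothesis. This stands as a choice of quantity, but the protocol does not state it, and by the Amendment 2 rationale it does not fit parathyroidectomy. A reader might infer that follow-up past transplant is also kept open for restarts. The documents say this for parathyroidectomy only. For transplant there is the general text of 9.2.5 and 9.3.1, and the worked example in 9.3.1 is a stop for hypocalcaemia.

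**Source.** The explicit rationale sits in an amendment summary. It is used here only for purpose and agrees with the current 9.2.5. The wording is that children may restart, not that they are expected to.

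**Counted as zero.** A reader might infer that a later restart is scored as a failure to restart, or lost from the study. Neither follows. Censoring is not a negative outcome, and later restarts could still be described outside the curve. Uncounted restarts and removed low-rate children also pull the curve in opposite directions.

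**Known upward bias.** Suppose an assumed restart rate of 0.5 per year and transplant rate of 0.2 to 0.4 per year. The two-year Kaplan-Meier value is 1 − exp(−1) = 63.2%, and restart before transplant is 53.8% to 46.4%. A reader might take that gap as the size of the error. It leaves out every restart after transplant and does not model parathyroidectomy. If transplanted children kept the same 0.5 rate, following them through would return 63.2%, leaving no gap.

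**Time origin.** This may properly be left to the SAP, so the loss of person-time is conditional. The censoring rule is not left open: the protocol fixes it.

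**Conclusion.** The point holds for parathyroidectomy on the text alone. The shared rule keeps off the curve any restart after that procedure, and the sponsor's stated reason for following past it is that such restarts may happen. This needs no assumption about rates.

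For transplant the conclusion is weaker. The rule assumes non-informative censoring without support, and the curve overstates restart among stoppers if transplanted children restart less often. The loss of person-time assumes that the clock starts at discontinuation and that the procedure falls on or before the stop date.

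Size and direction are unknown. The range of 1 to 25 points rests wholly on assumed inputs and on fewer restarts after procedures than after other stops. The change is worth making, but this is one descriptive output and does not undermine the registry.

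**What to change.** In sections 9.7.2.3.2 and 9.7.2.4, take re-initiation out of the shared rule and state that:

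- the clock starts at the discontinuation date;
- the analysis is not censored at parathyroidectomy;
- cumulative incidence of restart is shown, with death as a competing event;
- transplant is either followed through or treated as a competing event, with the choice stated, and is not handled as censoring;
- restarts are tabulated before and after each procedure and by reason for stopping.

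Reconcile section 9.3.1 in the same amendment. It says that treatment data end at first discontinuation and also that continued collection will capture re-initiation. As it stands, the first statement puts every restart date in doubt.

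The cost is a short wording change in two sections plus that reconciliation. Prescription dates, reasons for change and both procedures are already variables in 9.3.2, but restart dates can be relied on only once 9.3.1 is settled. The downside is a change in the quantity described: restart among all stoppers, and no longer only among those still on dialysis without a procedure. The before-and-after table keeps the narrower quantity visible.
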